6.2.3 Methods for Evaluation of Measurable Disease

All measurements should be taken and recorded in metric notation using a ruler or calipers. All baseline evaluations should be performed as closely as possible to the beginning of treatment and never more than 4 weeks before the beginning of the treatment.

The same method of assessment and the same technique should be used to characterize each identified and reported lesion at baseline and during follow-up. Imaging-based evaluation is preferred to evaluation by clinical examination unless the lesion(s) being followed cannot be imaged but are assessable by clinical exam.

Clinical lesions: Clinical lesions will only be considered measurable when they are superficial (e.g., skin nodules and palpable lymph nodes) and ≥ 10 mm diameter as assessed using calipers (e.g., skin nodules). In the case of skin lesions, documentation by color photography, including a ruler to estimate the size of the lesion, is recommended.

Chest x-ray: Lesions on chest x-ray are acceptable as measurable lesions when they are clearly defined and surrounded by aerated lung. However, CT is preferable.

Conventional CT and MRI: This guideline has defined measurability of lesions on CT scan based on the assumption that CT slice thickness is 5 mm or less. If CT scans have slice thickness greater than 5 mm, the minimum size for a measurable lesion should be twice the slice thickness. MRI is also acceptable in certain situations (e.g. for body scans).

Use of MRI remains a complex issue. MRI has excellent contrast, spatial, and temporal resolution; however, there are many image acquisition variables involved in MRI, which greatly impact image quality, lesion conspicuity, and measurement. Furthermore, the availability of MRI is variable globally. As with CT, if an MRI is performed, the technical specifications of the scanning sequences used should be optimized for the evaluation of the type and site of disease. Furthermore, as with CT, the modality used at follow-up should be the same as was used at baseline and the lesions should be measured/assessed on the same pulse sequence. It is beyond the scope of the RECIST guidelines to prescribe specific MRI pulse sequence parameters for all scanners, body parts, and diseases. Ideally, the same type of scanner should be used and the image acquisition protocol should be followed as closely as possible to prior scans. Body scans should be performed with breath-hold scanning techniques, if possible.

PET-CT: At present, the low dose or attenuation correction CT portion of a combined PET-CT is not always of optimal diagnostic CT quality for use with RECIST measurements. However, if the site can document that the CT performed as part of a PET-CT is of identical diagnostic quality to a diagnostic CT (with IV and oral contrast), then the CT portion of the PET-CT can be used for RECIST measurements and can be used interchangeably with conventional CT in

accurately measuring cancer lesions over time. Note, however, that the PET portion of the CT introduces additional data which may bias an investigator if it is not routinely or serially performed.

Ultrasound: Ultrasound is not useful in assessment of lesion size and should not be used as a method of measurement. Ultrasound examinations cannot be reproduced in their entirety for independent review at a later date and, because they are operator dependent, it cannot be guaranteed that the same technique and measurements will be taken from one assessment to the next. If new lesions are identified by ultrasound in the course of the study, confirmation by CT or MRI is advised. If there is concern about radiation exposure at CT, MRI may be used instead of CT in selected instances.

Endoscopy, Laparoscopy: The utilization of these techniques for objective tumor evaluation is not advised. However, such techniques may be useful to confirm complete pathological response when biopsies are obtained or to determine relapse in trials where recurrence following complete response (CR) or surgical resection is an endpoint.

Tumor markers: Tumor markers alone cannot be used to assess response. If markers are initially above the upper normal limit, they must normalize for a patient to be considered in complete clinical response. Specific guidelines for both CA-125 response (in recurrent ovarian cancer) and PSA response (in recurrent prostate cancer) have been published.³³⁻³⁵ In addition, the Gynecologic Cancer Intergroup has developed CA-125 progression criteria which are to be integrated with objective tumor assessment for use in first-line trials in ovarian cancer.³⁵

Cytology, Histology: These techniques can be used to differentiate between partial responses (PR) and complete responses (CR) in rare cases (e.g., residual lesions in tumor types, such as germ cell tumors, where known residual benign tumors can remain).

The cytological confirmation of the neoplastic origin of any effusion that appears or worsens during treatment when the measurable tumor has met criteria for response or stable disease is mandatory to differentiate between response or stable disease (an effusion may be a side effect of the treatment) and progressive disease.

FDG-PET: While FDG-PET response assessments need additional study, it is sometimes reasonable to incorporate the use of FDG-PET scanning to complement CT scanning in assessment of progression (particularly possible 'new' disease). New lesions on the basis of FDG-PET imaging can be identified according to the following algorithm:

- a. Negative FDG-PET at baseline, with a positive FDG-PET at follow-up is a sign of PD based on a new lesion.
- b. No FDG-PET at baseline and a positive FDG-PET at follow-up: If the positive FDG-PET at follow-up corresponds to a new site of disease confirmed by CT, this is PD. If the positive FDG-PET at follow-up is not confirmed as a new site of disease on CT, additional follow-up CT scans are needed to determine if there is truly progression occurring at that site (if so, the date of PD will be the date of the initial abnormal FDG-PET scan). If the positive FDG-PET at follow-up corresponds to a pre-existing site of disease on CT that is not progressing on the basis of the anatomic images, this is not PD.
- c. FDG-PET may be used to upgrade a response to a CR in a manner similar to a biopsy

in cases where a residual radiographic abnormality is thought to represent fibrosis or scarring. The use of FDG-PET in this circumstance should be prospectively described in the protocol and supported by disease-specific medical literature for the indication. However, it must be acknowledged that both approaches may lead to false positive CR due to limitations of FDG-PET and biopsy resolution/sensitivity.

Note: A ‘positive’ FDG-PET scan lesion means one which is FDG avid with an uptake greater than twice that of the surrounding tissue on the attenuation corrected image.

6.2.4 Response Criteria

6.2.4.1 Evaluation of Target Lesions

Complete Response (CR): Disappearance of all target lesions. Any pathological lymph nodes (whether target or non-target) must have reduction in short axis to <10 mm.

Partial Response (PR): At least a 30% decrease in the sum of the diameters of target lesions, taking as reference the baseline sum of diameters.

Progressive Disease (PD): At least a 20% increase in the sum of the diameters of target lesions, taking as reference the smallest sum on study (this includes the baseline sum if that is the smallest on study). In addition to the relative increase of 20%, the sum must also demonstrate an absolute increase of at least 5 mm. (Note: the appearance of one or more new lesions is also considered progressions).

Stable Disease (SD): Neither sufficient shrinkage to qualify for PR nor sufficient increase to qualify for PD, taking as reference the smallest sum of diameters while on study.

6.2.4.2 Evaluation of Non-Target Lesions

Complete Response (CR): Disappearance of all non-target lesions and normalization of tumor marker level. All lymph nodes must be non-pathological in size (<10 mm short axis).

Note: If tumor markers are initially above the upper normal limit, they must normalize for a patient to be considered in complete clinical response.

Non-CR/Non-PD: Persistence of one or more non-target lesion(s) and/or maintenance of tumor marker level above the normal limits.

Progressive Disease (PD): Appearance of one or more new lesions and/or *unequivocal progression* of existing non-target lesions. *Unequivocal progression* should not normally trump target lesion status. It must be representative of overall disease status change, not a single lesion increase.

Although a clear progression of “non-target” lesions only is exceptional, the opinion of the treating physician should prevail in such circumstances, and the progression status should be confirmed at a later time by the review panel (or Principal Investigator).

6.2.4.3 Evaluation of Best Overall Response

The best overall response is the best response recorded from the start of the treatment until disease progression/recurrence (taking as reference for progressive disease the smallest measurements recorded since the treatment started). The patient's best response assignment will depend on the achievement of both measurement and confirmation criteria.

Abbreviated Title: Phase II everolimus for BHD

Version Date: March 7, 2017

For Patients with Measurable Disease (i.e., Target Disease)

Target Lesions	Non-Target Lesions	New Lesions	Overall Response	Best Overall Response when Confirmation is Required*
CR	CR	No	CR	≥ 4 wks. Confirmation**
CR	Non-CR/Non-PD	No	PR	≥ 4 wks. Confirmation**
CR	Not evaluated	No	PR	
PR	Non-CR/Non-PD/not evaluated	No	PR	
SD	Non-CR/Non-PD/not evaluated	No	SD	Documented at least once ≥ 4 wks. from baseline**
PD	Any	Yes or No	PD	no prior SD, PR or CR
Any	PD***	Yes or No	PD	
Any	Any	Yes	PD	

* See RECIST 1.1 manuscript for further details on what is evidence of a new lesion.

** Only for non-randomized trials with response as primary endpoint.

*** In exceptional circumstances, unequivocal progression in non-target lesions may be accepted as disease progression.

Note: Patients with a global deterioration of health status requiring discontinuation of treatment without objective evidence of disease progression at that time should be reported as “*symptomatic deterioration*.” Every effort should be made to document the objective progression even after discontinuation of treatment.

For Patients with Non-Measurable Disease (i.e., Non-Target Disease)

Non-Target Lesions	New Lesions	Overall Response
CR	No	CR
Non-CR/non-PD	No	Non-CR/non-PD*
Not all evaluated	No	not evaluated
Unequivocal PD	Yes or No	PD
Any	Yes	PD

* 'Non-CR/non-PD' is preferred over 'stable disease' for non-target disease since SD is increasingly used as an endpoint for assessment of efficacy in some trials so to assign this category when no lesions can be measured is not advised

6.2.5 Duration of Response

Duration of overall response: The duration of overall response is measured from the time measurement criteria are met for CR or PR (whichever is first recorded) until the first date that recurrent or progressive disease is objectively documented (taking as reference for progressive disease the smallest measurements recorded since the treatment started).

The duration of overall CR is measured from the time measurement criteria are first met for CR until the first date that progressive disease is objectively documented.

Duration of stable disease: Stable disease is measured from the start of the treatment until the criteria for progression are met, taking as reference the smallest measurements recorded since the treatment started, including the baseline measurements.

6.3 TOXICITY CRITERIA

The following adverse event management guidelines are intended to ensure the safety of each patient while on the study. The descriptions and grading scales found in the revised NCI Common Terminology Criteria for Adverse Events (CTCAE) version 4.0 will be utilized for AE reporting. All appropriate treatment areas should have access to a copy of the CTCAE version 4.0. A copy of the CTCAE version 4.0 can be downloaded from the CTEP web site (http://ctep.cancer.gov/protocolDevelopment/electronic_applications/ctc.htm#ctc_40).

7 SAFETY REPORTING REQUIREMENTS/DATA AND SAFETY MONITORING PLAN

7.1 DEFINITIONS

7.1.1 Adverse Event

An adverse event is defined as any reaction, side effect, or untoward event that occurs during the course of the clinical trial associated with the use of a drug in humans, whether or not the event is considered related to the treatment or clinically significant. For this study, AEs will include events reported by the patient, as well as clinically significant abnormal findings on physical examination or laboratory evaluation. A new illness, symptom, sign or clinically significant laboratory abnormality or worsening of a pre-existing condition or abnormality is considered an AE. All AEs must be recorded on the AE case report form except for grade 1 AEs which can be excluded.

All AEs, including clinically significant abnormal findings on laboratory evaluations, regardless of severity, will be followed until return to baseline or stabilization of event. Serious adverse events that occur more than 30 days after the last administration of investigational agent/intervention and have an attribution of at least possibly related to the agent/intervention should be recorded and reported as per sections [7.2](#) and [7.3](#).

An abnormal laboratory value will be considered an AE if the laboratory abnormality is characterized by any of the following:

- Results in discontinuation from the study
- Is associated with clinical signs or symptoms
- Requires treatment or any other therapeutic intervention
- Is associated with death or another serious adverse event, including hospitalization.
- Is judged by the Investigator to be of significant clinical impact
- If any abnormal laboratory result is considered clinically significant, the investigator will provide details about the action taken with respect to the test drug and about the patient's outcome.

7.1.2 Suspected adverse reaction

Suspected adverse reaction means any adverse event for which there is a reasonable possibility that the drug caused the adverse event. For the purposes of IND safety reporting, 'reasonable possibility' means there is evidence to suggest a causal relationship between the drug and the adverse event. A suspected adverse reaction implies a lesser degree of certainty about causality than adverse reaction, which means any adverse event caused by a drug.

7.1.3 Unexpected adverse reaction

An adverse event or suspected adverse reaction is considered "unexpected" if it is not listed in the investigator brochure or is not listed at the specificity or severity that has been observed; or, if an investigator brochure is not required or available, is not consistent with the risk information described in the general investigational plan or elsewhere in the current application.

"Unexpected" also refers to adverse events or suspected adverse reactions that are mentioned in the investigator brochure as occurring with a class of drugs or as anticipated from the

Abbreviated Title: Phase II everolimus for BHD

Version Date: March 7, 2017

pharmacological properties of the drug, but are not specifically mentioned as occurring with the particular drug under investigation.

7.1.4 Serious

An Unanticipated Problem or Protocol Deviation is serious if it meets the definition of a Serious Adverse Event or if it compromises the safety, welfare or rights of subjects or others.

7.1.5 Serious Adverse Event

An adverse event or suspected adverse reaction is considered serious if in the view of the investigator or the sponsor, it results in any of the following:

- Death,
- A life-threatening adverse drug experience
- Inpatient hospitalization or prolongation of existing hospitalization
- Persistent or significant incapacity or substantial disruption of the ability to conduct normal life functions
- A congenital anomaly/birth defect.
- Important medical events that may not result in death, be life-threatening, or require hospitalization may be considered a serious adverse drug experience when, based upon appropriate medical judgment, they may jeopardize the patient or subject and may require medical or surgical intervention to prevent one of the outcomes listed in this definition.

7.1.6 Disability

A substantial disruption of a person's ability to conduct normal life functions.

7.1.7 Life-threatening adverse drug experience

Any adverse event or suspected adverse reaction that places the patient or subject, in the view of the investigator or sponsor, at immediate risk of death from the reaction as it occurred, i.e., it does not include a reaction that had it occurred in a more severe form, might have caused death.

7.1.8 Protocol Deviation (NIH Definition)

Any change, divergence, or departure from the IRB-approved research protocol.

7.1.9 Non-compliance (NIH Definition)

The failure to comply with applicable NIH Human Research Protections Program (HRPP) policies, IRB requirements, or regulatory requirements for the protection of human research subjects.

7.1.10 Unanticipated Problem

Any incident, experience, or outcome that:

- Is unexpected in terms of nature, severity, or frequency in relation to
 - (a) the research risks that are described in the IRB-approved research protocol and informed consent document; Investigator's Brochure or other study documents, and

Abbreviated Title: Phase II everolimus for BHD

Version Date: March 7, 2017

(b) the characteristics of the subject population being studied; **AND**

- Is related or possibly related to participation in the research; **AND**
- Suggests that the research places subjects or others at a *greater risk of harm* (including physical, psychological, economic, or social harm) than was previously known or recognized.

7.2 INVESTIGATOR REPORTING: NOVARTIS INSTRUCTIONS FOR RAPID NOTIFICATION OF SERIOUS ADVERSE EVENTS

All serious adverse events must be reported to Novartis Pharmaceuticals Drug Safety and Epidemiology Department (DS&E) and reporting will be done via the Investigators or his/her designee.

All events must be reported, by [contact]) to Novartis Pharmaceuticals DS&E Department within 24 hours of learning of its occurrence. This includes all serious, related, not related, labelled (expected) and unlabelled (unexpected) adverse experiences.

All deaths during treatment or within 30 days following completion of active protocol therapy must be reported within 24 hours.

Any serious adverse event occurring after the patient has provided informed consent and until 4 weeks after the patient has stopped study participation must be reported. This includes the period in which the study protocol interferes with the standard medical treatment given to a patient (e.g. treatment withdrawal during washout period, change in treatment to a fixed dose of concomitant medication).

Serious adverse events occurring more than 4 weeks after study discontinuation need only be reported if a relationship to the Novartis study drug (or therapy) is suspected.

For Comparator Drugs/Secondary Suspects (Concomitant Medications), all serious adverse experiences will be forwarded to the product manufacturer by the investigator.

7.2.1 Pregnancies

Any pregnancy that occurs during study participation should be reported by the site. To ensure patient safety each pregnancy must also be reported to Novartis within 24 hours of learning of its occurrence. The pregnancy should be followed up to determine outcome, including spontaneous or voluntary termination, details of birth, and the presence or absence of any birth defects, congenital abnormalities or maternal and newborn complications.

Pregnancy should be recorded on a Clinical Study Pregnancy Form and reported by the investigator to the oncology Novartis Drug Safety and Epidemiology (DS&E) department. Pregnancy follow-up should be recorded on the same form and should include an assessment of the possible relationship to the Novartis study treatment of any pregnancy outcome. Any SAE experienced during pregnancy must be reported on the SAE Report Form.

Abbreviated Title: Phase II everolimus for BHD

Version Date: March 7, 2017

Pregnancy outcomes must be collected for the female partners of any males who took study treatment in this study. Consent to report information regarding these pregnancy outcomes should be obtained from the mother.

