The potential reproductive risk for humans is unknown. However, due to the observed malformations in rats, everolimus should be considered potentially teratogenic. Everolimus should not be given to pregnant women unless the potential benefit outweighs the potential risk for the fetus. Women of childbearing potential should be advised to use highly effective contraception methods while they are receiving everolimus and up to 8 weeks after treatment has been stopped. It is not known whether everolimus is excreted in human milk. In animal studies, everolimus and/or its metabolites were readily transferred into the milk of lactating rats. Therefore, women who are taking everolimus should not breastfeed.

Additional information about everolimus can be found in the Affinitor package insert.

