2.1.2.10 Patients, who in the opinion of the investigator, are unlikely to comply with follow-up visits or other study requirements. Patients who are currently part of or have participated in any clinical investigation with an investigational drug within 1 month prior to dosing.

2.1.2.11 Pregnant or nursing (lactating) women.

2.1.2.12 Women of child-bearing potential (WOCBP), defined as all women physiologically capable of becoming pregnant, who do not agree to use highly effective methods of contraception during the study and 8 weeks after.

Highly effective contraception methods include combination of any two of the following:

- a. Use of oral, injected or implanted hormonal methods of contraception or;
- b. Placement of an intrauterine device (IUD) or intrauterine system (IUS);
- c. Barrier methods of contraception: condom or occlusive cap (diaphragm or cervical/vault caps) with spermicidal foam/gel/film/cream/ vaginal suppository;
- d. Total abstinence or;
- e. Male/female sterilization.

Women are considered post-menopausal and not of child-bearing potential if they have had 12 months of natural (spontaneous) amenorrhea with an appropriate clinical profile (e.g. age appropriate, history of vasomotor symptoms) or have had surgical bilateral oophorectomy (with or without hysterectomy) or tubal ligation at least six weeks prior to randomization. In the case of oophorectomy alone, only when the reproductive status of the woman

Abbreviated Title: Phase II everolimus for BHD

Version Date: March 7, 2017

has been confirmed by follow up hormone level assessment is she considered not of child-bearing potential.

2.1.2.13 Male patients whose sexual partner(s) are WOCBP who are not willing to use adequate contraception, during the study and for 8 weeks after the end of treatment.

2.1.2.14 Prior invasive malignancy of other histology currently requiring treatment.

2.1.2.15 Patients with active Hepatitis B (detectable HBV-DNA or HBsAg +) or Hepatitis C infection (detectable HCV RNA by PCR)

2.1.2.16 Patients who are currently on or have used potent or moderate inhibitors or strong inducers CYP3A4 or PgP inhibitors in the past 2 weeks

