3.4 STUDY CALENDAR

1 cycle = 28 days

Evaluations below may be performed within \pm 3 days of indicated time in order to accommodate patient schedules, holidays and weather emergencies. Imaging studies and optional tumor biopsies may be performed within \pm 7 days of indicated time.

Baseline and Restaging evaluation will be performed at the NIH CC. However, mandated laboratory studies and other evaluations may be performed at local laboratory or by local health care providers.

Restaging will be performed approximately every 12 weeks. Treatment can continue for 52 weeks in the absence of unacceptable toxicity or disease progression.

Patients with BHD associated tumors localized to the kidneys will be treated for one year in the absence of unacceptable toxicity or disease progression. Patients with locally advanced or metastatic disease will be treated until disease progression in the absence of unacceptable toxicity.

Abbreviated Title: Phase II everolimus for BHD

Version Date: March 7, 2017

	Screening / Baseline	Day 1	Cycle 1 Day 14	Cycle 2 Day 1	Cycle 2 Day 14	Cycle 3 Day 1	Cycle 3 Day 14	Cycle 4 Day 1	Start of Every Cycle	EOT	Follow up ¹¹	Survival ¹²
Visit no.	1	2	3	4	5	6	7	8	9, 10 etc...		EOT + 28 days	
Treatment days	-14 to -1											
Demography/informed consent	X											
Relevant medical history/current medical conditions	X											
Diagnosis and extent of cancer	X											
Vital signs	X	X*		X		X		X	X	X		
Height	X											
Weight	X	X*		X		X		X	X	X	X	
Physical examination	X ⁸											
ECOG/Karnofsky performance status	X	X*										
EKG ¹	X											
Thyroid function tests	X		Every 12 weeks									
CBC with differential	X		X	X		X		X	X	X	X	
Serum Chemistries ²	X		X	X		X		X	X	X	X	
Fasting serum Lipid Profile ³	X			X		X		X	X	X		
Urinalysis ⁴	X			X		X		X	X			
Serum β hCG (in female patients of childbearing potential)	X			X		X		X	X			
HbA1c, pulse oximetry	X											
PT/PTT	X											

Abbreviated Title: Phase II everolimus for BHD

Version Date: March 7, 2017

	Screening / Baseline	Day 1	Cycle 1 Day 14	Cycle 2 Day 1	Cycle 2 Day 14	Cycle 3 Day 1	Cycle 3 Day 14	Cycle 4 Day 1	Start of Every Cycle	EOT	Follow up ¹¹	Survival ¹²
Visit no.	1	2	3	4	5	6	7	8	9, 10 etc...		EOT + 28 days	
Treatment days	-14 to -1											
Prior/concomitant medications	X											
Adverse events												
Tumor evaluation												
PFT	X											
CT chest/abdomen/pelvis and/or, CT chest plus MRI abdomen/pelvis ⁵	X									X		

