5. Chest, abdomen, pelvis scans need to be repeated at each tumor assessment visit (including if negative at baseline). Scans for complete and partial responses must be repeated at least at 4 weeks but no later than the next scheduled tumor assessment following the first documented response. Skin lesions should be photographed in addition to measuring.																								
6. CT Neck in patients with known or suspected metastatic disease in the neck will be repeated at restaging if positive for metastasis.																								
7. A bone scan or skeletal survey is to be performed at baseline and will be repeated at restaging if positive for metastasis.																								
8. Repeat at restaging only if indicated																								
9. All patients should be screened for hepatitis risk factors and any past illnesses of hepatitis B and hepatitis C as outlined in Sections 2.2. Patients with viral hepatitis B or C risk factors should be screened for Hep B and HCV RNA-PCR.																								
10. Patients on antiviral prophylaxis treatment or positive HBV antibodies should be tested for HBV-DNA every 3 – 4 weeks. Patients with positive HCV-RNA PCR or a history of past infection, even if treated and considered 'cured' – should be followed by HCV-RNA PCR every 4 – 8 weeks.																								
11. Follow up visits conducted at the EOT+28 days visit.																								
12. After progression, an attempt will be made to follow patients to obtain information about survival every three to six months.																								
Legend: wks stands for weeks, EOT for End of Treatment visit																								
13. Photographic evaluation of skin lesions - only in patients with BHD- associated cutaneous manifestations.																								

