10.6 CONSENT AND ASSENT PROCESS AND DOCUMENTATION

The investigator must explain to each subject the nature of the study, its purpose, the procedures involved, the expected duration, the potential risks and benefits involved and any discomfort it may entail. Each subject must be informed that participation in the study is voluntary and that he/she may withdraw from the study at any time and that withdrawal of consent will not affect his/her subsequent medical treatment or relationship with the treating physician.

This informed consent should be given by means of a standard written statement, written in non-technical language. The subject should read and consider the statement before signing and dating it, and should be given a copy of the signed document. If the subject cannot read or sign the documents, oral presentation may be made or signature given by the subject's legally appointed representative, if witnessed by a person not involved in the study, mentioning that the patient could not read or sign the documents. No patient can enter the study before his/her informed consent has been obtained.

The informed consent form is considered to be part of the protocol, and must be submitted by the investigator with it for IRB approval.

Fertile men and women of child bearing potential should be informed that taking the study medication may involve unknown risks to the fetus if pregnancy were to occur during the study and agree that in order to participate in the study they must adhere to the contraception requirement for the duration of the study. If there is any question that the patient will not reliably comply, they should not be entered in the study.

For the optional research biopsy, the patient will consent at the time of the procedure. If the patient refuses the optional biopsy at that time, the refusal will be documented in the medical record and in the research record.

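### Pregnancy testing, safety visits and the pregnancy-reporting window do not match the protocol's own 8-week post-treatment contraception period

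*Combined protocol and SAP*

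**What the plan says.** **Risk and contraception.** Section 1.2.3.2 describes embryo and fetal toxicity in rats, says the drug should be regarded as possibly teratogenic, and advises women to use contraception "while they are receiving everolimus and up to 8 weeks after treatment has been stopped". Section 2.1.2 carries the same length in two forms. For women of child-bearing potential (2.1.2.12) the requirement is "contraception during the study and 8 weeks after". For men with partners of child-bearing potential (2.1.2.13) it is "during the study and for 8 weeks after the end of treatment". Section 10.6 says of fertile men and women that "they must adhere to the contraception requirement for the duration of the study", and names no period after it.

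**Testing.** In the Section 3.4 calendar, the row that begins "Serum β hCG (in female patients of childbearing potential" is marked at screening, on day 1 of cycles 2, 3 and 4, and at the start of every later cycle. Its end-of-treatment (EOT) and EOT+28-day cells are empty. The blood count and chemistry rows are marked in both. The post-treatment assessments in Section 3.5 include no pregnancy test.

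**Visits.** Calendar footnote 11 reads "Follow up visits conducted at the EOT+28 days visit". Section 3.5 puts the safety visit at 4 to 5 weeks after the drug stops. Footnote 12 adds survival contact every three to six months, after progression.

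**Reporting.** Section 7.2.1 states: "Any pregnancy that occurs during study participation should be reported by the site". Such a pregnancy goes to the manufacturer within 24 hours and is followed to outcome. Outcomes in partners of treated men must also be collected, with no end date given. Section 7.2 covers serious adverse events (SAEs) until 4 weeks after participation stops, and later ones if the drug is suspected. Section 7.1.5 counts a congenital anomaly as an SAE.

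**The concern.** The 8 weeks are the protocol's own statement of how long conception should be avoided after exposure. If conception in that time matters enough to require contraception, a pregnancy in that time matters enough to be looked for and reported. Section 7.2.1 supports this, because it requires follow-up to birth or loss.

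Followed as written, the plan leaves two openings. A pregnancy that begins in the last treatment cycle, while the patient is still taking the drug, has no scheduled test to find it. A pregnancy that begins late in the 8 weeks need not be reported under a natural reading of 7.2.1. Either could leave an exposed pregnancy without the outcome follow-up that the protocol calls for. The stake is patient safety and the completeness of the safety record. The efficacy analysis is not affected.

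**Working it through.** The plan states no figure to reproduce here. The check is day arithmetic on its own windows, counting the first dose as day 1, taking visits on their nominal days and EOT as the last dose.

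**Inputs.** Cycle length is 28 days and treatment for localized disease lasts up to 52 weeks (Section 3.4). Post-treatment contraception lasts 8 weeks (1.2.3.2, 2.1.2.13). The safety visit is at 28 days (footnote 11) or up to 5 weeks, that is 35 days (3.5).

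**1. Time without a scheduled test, full course.**
- Treatment: 52 × 7 = 364 days; 364 / 28 = 13 cycles.
- Last scheduled βhCG, day 1 of cycle 13: 364 − 28 + 1 = day 337.
- End of the 8 weeks: 364 + 8 × 7 = 364 + 56 = day 420.
- Gap: 420 − 337 = 83 days, made up of 27 days to the last dose plus the whole 56.

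**2. Time without a scheduled test, early stop.** No test is tied to EOT. A patient whose last dose falls on cycle day d has a gap of (d − 1) + 56 days. For d from 1 to 28 this runs from 56 to 83 days.

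**3. Time without a scheduled visit** (localized patient, therapy completed, no progression).
- Visit at 28 days: 56 − 28 = 28 days; 28 / 56 = 50%.
- Visit at 35 days: 56 − 35 = 21 days; 21 / 56 = 37.5%.

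**4. Reporting of patients' pregnancies.** Because study participation is undefined, the shortfall against day 420 depends on the reading assumed:
- participation ends with the last dose (day 364): 56 days;
- it ends at the safety visit (day 392 or 399): 28 or 21 days;
- it runs through the 8 weeks: none.

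Two passages make the last reading the least natural. Section 2.1.2.12 describes the 8 weeks as coming after the study. Section 7.2 gives SAEs a 4-week tail once participation has stopped, while 7.2.1 gives pregnancies none.

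**5. Contraception duration.** Sections 1.2.3.2 and 2.1.2.13 count 8 weeks from the end of treatment, 2.1.2.12 counts 8 weeks from the end of the study, and 10.6 has no tail. Suppose, for illustration only, that the study ends for a patient at the 28-day visit (364 + 28 = day 392). The stated ends are then day 420, day 392 + 56 = 448, and day 392.

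**6. With βhCG added at EOT and EOT+28.** Tests would fall on days 337, 364 and 392. The intervals become 27, 28 and, to day 420, 28 days, in place of one of 83.

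**The case against.** The strongest reply is that nothing obliges tests or visits to last as long as contraception. A contraception period that outlasts the visits is not in itself a contradiction. On-treatment testing also has its own purpose, since a positive test ends therapy (Section 3.6.1), and after EOT there is no therapy to end. This is fair as far as it goes. It does not explain why the last cycle, spent on drug, closes without a test, or why a duty to report and follow pregnancies has no defined end.

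Several stronger readings are tempting, and the documents do not support them.

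- **That the 28-day visit is the last contact.** It is the last scheduled safety visit, and 3.5 allows up to 5 weeks. Unresolved grade 3 and 4 events are followed, and survival contact continues after progression. That survival contact is not stated for a patient who completes without progression, and no pregnancy check is listed with it.
- **That a patient goes off study at week 56 with no duty to report.** Section 3.6.2 ends the study on completion of a follow-up period of unstated length. The absence of a duty is one reading of an undefined term.
- **That partner pregnancies are a gap.** Their outcome collection is open-ended, so it is broader than 8 weeks.
- **That late birth defects go unreported.** A congenital anomaly is an SAE, and late SAEs stay reportable if the drug is suspected. This does depend on the site learning of the event, and it does not capture normal births or early losses.
- **That patients are told the wrong duration at consent.** Section 10.6 refers to the contraception requirement, which may mean the one in 2.1.2. The consent form is not in the copy reviewed, so only the wording of 10.6 can be faulted.

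Empty calendar cells also need care, because the adverse-event row is empty throughout. Here the βhCG row reads coherently, neighbouring laboratory rows are marked at EOT and EOT+28, and the list in 3.5 agrees. The history and physical examination at EOT+28 give a pregnancy some chance to come to light, but they do not replace a test.

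**Conclusion.** The point holds as a mismatch between the protocol's stated contraception period and its surveillance and reporting rules. No βhCG is scheduled after the start of the last cycle, which leaves 83 days untested after a full 52-week course. The last scheduled safety visit leaves 21 to 28 of 56 days (37.5 to 50%) without a visit for a localized patient who completes without progression. Patient pregnancy reporting hangs on an undefined term, with a shortfall of 0 to 56 days depending on how it is read. The contraception duration is worded inconsistently across 1.2.3.2, 2.1.2 and 10.6.

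These figures assume nominal visit days (Section 3.4 allows 3 days either way), uninterrupted 28-day cycles, and 8 weeks counted from the last dose. Few patients are concerned: accrual is capped at 18, median age at renal cancer onset is given as about 50, and the number of women of child-bearing potential is not stated. The two-stage design in Section 8 is unaffected. It merits correction because the possible harm is serious and the remedy is cheap.

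**What to change.** 1. In Section 7.2.1, state the start and end of the reporting window for patients' pregnancies, so that it covers the protocol's own post-treatment contraception period, and define when study participation ends. This costs wording only.
2. In the Section 3.4 calendar and the Section 3.5 list, add serum βhCG for women of child-bearing potential at EOT and EOT+28, using blood already scheduled for counts and chemistry. The cost is one extra assay at each of two visits. A test at EOT+28 cannot detect a conception in the weeks after it, so the reporting window in item 1 has to cover those.
3. Reconcile the contraception duration in 1.2.3.2, 2.1.2.12, 2.1.2.13 and 10.6, including whether it is counted from the end of treatment or the end of the study. Which duration and anchor apply is for the sponsor and investigator to settle. The consent form should then be checked against the result.

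Partner-outcome collection and late SAE reporting need no extension.
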